#### 4.8.4.3 NPI Total Scores

The NPI is a validated, reliable, multi-item instrument to assess psychopathology in AD based on interview with the study partner. The NPI evaluates both the frequency and severity of 12 neuropsychiatric features, including delusions, hallucinations, agitation/aggression, dysphoria, anxiety, euphoria, apathy, disinhibition, irritability/lability, and aberrant motor behavior, as well as evaluates sleep and appetite/eating disorders. Frequency assessments range from 1 (occasionally, less than once per week) to 4 (very frequently, once or more per day or continuously) as well as severity (1 = mild, 2 = moderate, 3 = severe). The overall score and the score for each subscale are the product of severity and frequency. This treatment effect will be summarized as the difference in change from baseline in the NPI total score between the BVH-4157 and placebo groups.

As for the primary endpoint, the change from baseline in NPI total score will be analyzed using the mITT set via a MMRM analysis model using the same approach as in the primary analysis.

As a further exploratory analysis, for Mild vs Moderate MMSE baseline status subgroups an MMRM analysis will be utilized on each subgroup using the model specification as described above.

In the event that an NPI is partially, but not completely administered, individual NPI scores will be imputed within the scoring algorithm using the following guidelines:

- If there are 4 or fewer items with missing data on an NPI (severity and/or frequency), and if the participant has a previous or subsequent complete NPI, the scores for each missing item will be used from the assessment completed on the date closest to the assessment with missing data (either the previous NPI or subsequent NPI) in order to calculate a total score.
- If 5 or more questions are missing, the entire assessment will be considered as missing.

The NPI will be assessed at visits conducted in clinic or via remote communication. Only inclinic assessments will be considered in the primary analysis; sensitivity analysis will include a similar analysis including remote assessments.

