#### 4.8.4.4 MMSE Scores

The MMSE is a validated, brief, frequently used screening instrument for Alzheimer's disease drug studies. The MMSE scale evaluates orientation, memory, attention, concentration, naming, repetition, comprehension, and ability to create a sentence and to copy two overlapping pentagons. The MMSE is scored as the number of correctly completed items with a lower score indicative of poorer performance and greater cognitive impairment. The total score ranges from 0 (worse) to 30 (perfect performance).

When computing the total score, if three or fewer of the 30 items on the MMSE are missing, the last non-missing observation for those items will be carried forward in order to calculate a total score. If four or more items are missing, the MMSE Total Score will be missing.

The change from baseline in MMSE Total Score will be analyzed using the mITT set via a MMRM analysis model, similar to the primary endpoint.

As a further exploratory analysis, for Mild vs Moderate MMSE status subgroups an MMRM analysis will be utilized on each subgroup using the model specification as described above.

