#### 4.8.5 Exploratory Efficacy Endpoints

#### 4.8.5.1 MoCA Scores

The MoCA is a brief mental status screening instrument that evaluates orientation, memory, executive functions, visuospatial ability, language, abstraction, attention, and naming.

When computing the total score, if three or fewer of the 30 items on the MoCA are missing, the last non-missing observation for those items will be carried forward to compute a total score. If four or more items are missing, the MoCA Total Score will be missing.

The change from baseline in MoCA Total Score will be analyzed using the mITT set via a MMRM analysis model.

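### The NPI item-fill rule lets on-treatment item scores enter the baseline total, contrary to the SAP's own definition of baseline

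*SAP*

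**What the plan says.** SAP 4.8.4.3 allows a partly completed NPI to be scored when no more than four items are missing and "if the participant has a previous or subsequent complete NPI". In that case "the scores for each missing item will be used from the assessment completed on the date closest to the assessment with missing data". The donor must be complete, but it is not restricted by visit or by treatment status. Above the limit the form is not scored: "If 5 or more questions are missing, the entire assessment will be considered as missing".

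NPI change from baseline is then analysed with the same mixed model as the co-primary endpoints. That model (SAP 4.3.3 and 4.8.3) has the baseline score and its interaction with visit as fixed effects. NPI is one of four secondary efficacy endpoints tested by the Holm procedure once both co-primaries are significant (SAP 4.3.4; Protocol 12.4).

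SAP 4.3.1.2 and the note to Table 2 in SAP 4.3.8 define baseline as the latest assessment dated no later than the day study drug starts. SAP 4.3.7 rules out imputation in the main efficacy analyses unless a section says otherwise, and 4.8.4.3 is such an exception.

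MMSE and MoCA follow a different rule. For MMSE, "if three or fewer of the 30 items on the MMSE are missing, the last non-missing observation for those items will be carried forward". For MoCA, "if three or fewer of the 30 items on the MoCA are missing, the last non-missing observation for those items will be carried forward".

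**The concern.** A baseline value should be fixed before treatment can act on it. Under the NPI rule the form keeps its pre-dose date, but part of its total can be made of item scores recorded after months of treatment. In the active arm those items can carry drug effect; in the placebo arm they cannot. The value is then used twice: it is subtracted to form the change score, and it enters the model as a covariate. A covariate that can depend on treatment weakens the usual justification for adjusting on it, and the subtraction removes part of the effect being estimated.

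Elsewhere the SAP treats a post-dose baseline as something to be justified. The note to Table 1 in SAP 4.3.8 extends the CDR baseline window to Day 2 because of one participant, on the ground that so little treatment had been given. That reasoning cannot cover an item score taken at Week 24 or Week 48.

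**Working it through.** **Step 1: which donors exist for an incomplete baseline NPI?**

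- Protocol 8.1.1 (screening) does not list NPI.
- Protocol 8.1.2, 8.1.7 and 8.1.9 list it at baseline, Week 24 and Week 48 or early termination. The double-blind schedule in Appendix I agrees.
- The extension schedule does not list it.

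No scheduled pre-dose donor exists, so every scheduled donor is on treatment or later.

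**Step 2: what happens to one item under each missing pattern?** Scheduled days are 0, 168 and 336. B, W24 and W48 are the item's scores at the three visits.

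| NPI item missing at | Donor | Change to Week 24 | Change to Week 48 | Post-dose value in baseline? |
|---|---|---|---|---|
| Baseline | Week 24 | 0 | W48 − W24 | Yes |
| Week 24 | Baseline or Week 48 (tied at 168 days) | 0, or W48 − B | W48 − B | No |
| Week 48 | Week 24 | W24 − B | W24 − B | No |
| Baseline and Week 24 | Week 48 | 0 | 0 | Yes |
| Baseline and Week 48 | Week 24 | 0 | 0 | Yes |
| Week 24 and Week 48 | Baseline | 0 | 0 | No |

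The first row is the core case: the first 24 weeks of change drop out of the endpoint, while the last 24 weeks remain. Change to Week 48 is exactly zero only when the baseline and Week 48 values come from the same form. That needs at least two of the three forms to be incomplete or absent.

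**Step 3: the same check for MMSE and MoCA.** Their items move forward in time only, so no pattern places a later score into baseline. A missing baseline MMSE item also has a pre-dose source, because MMSE is done at screening (Protocol 8.1.1). A missing baseline MoCA item has no earlier source and stays missing.

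**Step 4: size on one form.** With 12 domains each scored up to 4 × 3 = 12, four filled domains are 4/12 = 33% of the domains and 48 of 144 points.

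**Step 5: size on the Week 48 contrast.** The plan states no figure to reproduce, and the documents give no item-missingness rate, so these inputs are assumptions:

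- f, the share of participants with a baseline filled from Week 24: 1% to 10%
- k, the number of domains filled: 1 to 4
- d24/d48, the true Week 24 effect over the true Week 48 effect: 0 to 1
- the effect is spread equally over the 12 domains

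An affected active participant shows d48 − (k/12) × d24 instead of d48. Averaged over the arm:

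proportional loss = f × (k/12) × (d24/d48)

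- Lowest: 0%, when d24/d48 = 0.
- Half the effect present by Week 24: from 0.01 × 1/12 × 0.5 = 0.04% to 0.10 × 4/12 × 0.5 = 1.67%.
- Highest: 0.10 × 4/12 × 1 = 3.33%.

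This is for the unadjusted change score. If the slope of change on baseline is b, the arms' mean baselines also differ by f × (k/12) × d24. To first order, adjustment then multiplies the loss by (1 + b). With b between −1 and 0, the figures above are upper values for the assumed inputs.

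**The case against.** The case should be rare. Protocol 8.1.2 puts NPI on the baseline list and gives the first dose only after everything on the list is done, so an incomplete baseline NPI followed by dosing departs from procedure. The rule is the same in both arms. NPI is formally tested only if both co-primaries succeed. The same person's score on the same item at another visit may also be a better guess than the average of other behaviours, since the NPI domains are distinct. All of this stands and limits the size. It does not remove the contradiction: the rule was written for incomplete forms, and applying one rule to both arms does not make a post-dose score a baseline score.

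Other donors are possible: early termination, unscheduled and remote assessments may also yield an NPI. For a baseline item, such forms obtained after dosing have the same fault.

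The 33% ceiling depends on what an item is. The SAP speaks of items lacking severity and/or frequency, then of questions. If severity and frequency count separately, four missing entries could be two domains, or 2/12 = 17%.

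A reader might go further and infer that the fills force change to zero, or that all three scales have contaminated baselines. The documents support neither. A single baseline fill from Week 24 leaves W48 − W24, and MMSE and MoCA items are carried forward only. A reader might also want the whole NPI rescaled whenever items are missing. With four of 12 domains missing that is a factor of 12/8 = 1.5, beyond the SAP's 25% caps for other scales, and the trade-off is debatable.

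**Conclusion.** The NPI item-fill rule is wrong as written. It permits post-dose item scores in a baseline total that the SAP elsewhere requires to be pre-dose, and that total enters both the change score and the covariate of a Holm-tested secondary endpoint. The fault at baseline is confined to NPI.

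The effect on the result is probably small: a loss of 0% to 3.33% of the Week 48 NPI contrast under the assumed ranges. It would be larger if more participants were affected, if the missing domains carried more than an equal share of the effect, or if the effect were greater at Week 24 than at Week 48. The usual direction is toward no difference, but it depends on the time course of the effect, which the documents do not give. The reason to act is that the rule contradicts the baseline definition and is cheap to correct.

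**What to change.** Amend SAP 4.8.4.3 before database lock to say:

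- A baseline NPI item is never filled from an assessment made after the first dose, whether scheduled, early-termination, unscheduled or remote.
- If there is no pre-dose donor, the baseline total is prorated within the form under a cap such as the 25% that SAP 4.8.4.2 uses for ADCS-ADL. For 12 domains this allows at most 3 missing, with the total multiplied by 12/(12 − k), at most 12/9 = 1.33.
- Above the cap, the baseline total is missing.
- An item means a domain, missing if its severity or frequency is missing, so that the limits are unambiguous.

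The cost is a few sentences of SAP text and a change to the scoring code. A few participants may rely on within-form proration, which assumes that unanswered domains resemble answered ones; that is a weaker assumption for NPI than for a more uniform scale, hence the cap. Others may lose their baseline NPI total and drop out of the NPI model. They would stay in the mITT population, because SAP 3.1 defines it by the co-primary baselines and not by NPI.

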#### 4.8.4.4 MMSE Scores

The MMSE is a validated, brief, frequently used screening instrument for Alzheimer's disease drug studies. The MMSE scale evaluates orientation, memory, attention, concentration, naming, repetition, comprehension, and ability to create a sentence and to copy two overlapping pentagons. The MMSE is scored as the number of correctly completed items with a lower score indicative of poorer performance and greater cognitive impairment. The total score ranges from 0 (worse) to 30 (perfect performance).

When computing the total score, if three or fewer of the 30 items on the MMSE are missing, the last non-missing observation for those items will be carried forward in order to calculate a total score. If four or more items are missing, the MMSE Total Score will be missing.

The change from baseline in MMSE Total Score will be analyzed using the mITT set via a MMRM analysis model, similar to the primary endpoint.

As a further exploratory analysis, for Mild vs Moderate MMSE status subgroups an MMRM analysis will be utilized on each subgroup using the model specification as described above.

#### 4.8.5 Exploratory Efficacy Endpoints

#### 4.8.5.1 MoCA Scores

The MoCA is a brief mental status screening instrument that evaluates orientation, memory, executive functions, visuospatial ability, language, abstraction, attention, and naming.

When computing the total score, if three or fewer of the 30 items on the MoCA are missing, the last non-missing observation for those items will be carried forward to compute a total score. If four or more items are missing, the MoCA Total Score will be missing.

The change from baseline in MoCA Total Score will be analyzed using the mITT set via a MMRM analysis model.

#### 4.8.5.2 Composite Neuropsychological Test Battery Score

A cognitive composite outcome measure will be computed using measures from the NACC Neuropsychological Test Battery. The composite outcome will comprise the overall average of the Z-scores from each of the following NACC subtest measures: Craft Story 21 total immediate Recall; Craft Story 21 total delayed recall; Benson Figure copy score; Benson Figure delayed recall; Multilingual Naming Test total correct; Letter Fluency total score; Category Fluency total score; Trail Making Test A time to completion; Trail Making Test B time to completion; Number Span Forward total correct; and Number Span Backward total correct. Z-scores for each participant on each measure will be calculated using the overall average of all participants at baseline as reference.

The total composite neuropsychological test battery score will be calculated as the overall average Z-score from each of the completed subtests. If more than 2 NACC Neuropsychological Test Battery subtest measures are missing, the total composite neuropsychological test battery score will be missing. Please refer to Appendix 3 regarding prorating subtest scores when there are partially (i.e., item-level) missing data.

The change from baseline in composite neuropsychological test battery score will be analyzed using the mITT set via a mixed model as above. However since there are no repeated measures on participants, there will not be a participant-level random effect. This analysis is exploratory for potential publication purposes only.

In addition, descriptive statistics will also be presented by visit in the Open Label Extension Phase, by original randomized group (BHV-4157 and Placebo to BHV4157).

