9.1.4.4 Trail Making Test (Trails A and B)

The Trail Making Test is a test of processing speed and executive function. Trails A consists of 25 circles numbered 1 through 25 distributed over a white sheet of paper. The participant is instructed to draw a line to connect the circles in ascending numerical order as quickly as possible (150 second maximum). Trails B consists of 25 circles containing either numbers (1 through 13) or letters (A through L) that are randomly distributed across the page, and participants are instructed to connect the circles in alternating and ascending order (e.g., 1 to A; 2 to B). Performance is judged in terms of time to complete each trial. Time to complete Trails B (300 second maximum),

adjusted for the time taken to complete Trails A to control for sensorimotor demands of the task, is a sensitive measure of executive function and working memory.

9.1.4.5 *Verbal Fluency – Category Fluency*

Category fluency assesses semantic memory and language fluency in which participants name as many different exemplars of a given semantic category as rapidly as possible. Participants will be given 60 seconds to name exemplars in each of two categories: animals and vegetables.

9.1.4.6 *Verbal Fluency – Phonemic Fluency*

Phonemic Fluency is a measure of word generation that may be sensitive to dysfunction in the dominant frontal lobe. Participants will be given 60 seconds to name exemplars that begin with each of the two letters: F and L.

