# APPENDIX 3 - Calculating the composite neuropsychological test battery score when there are missing data

A cognitive composite outcome measure will be computed using measures from the NACC Neuropsychological Test Battery. The composite outcome will comprise the overall average of the Z-scores from each of the following NACC subtest measures: Craft Story 21 total immediate Recall; Craft Story 21 total delayed recall; Benson Figure copy score; Benson Figure delayed recall; Multilingual Naming Test total correct; Letter Fluency total score; Category Fluency total score; Trail Making Test A time to completion; Trail Making Test B time to completion; Number Span Forward total correct; and Number Span Backward total correct. Z-scores for each participant on each measure will be calculated using the overall average of all participants at baseline as reference.

Missing total scores for subtest measures from the NACC Neuropsychological Test Battery are designated as missing for the following reasons:

- Participant Unable for Cognitive Reasons
- • Participant Unable for Other Reasons (Physical, auditory, etc.)
- · Participant/Study Partner Refused
- · Oversight
- · Other Reason
- · Unknown

When total scores for subtest measures are missing because the participant was unable to complete the task for cognitive reasons, the worst possible score for the measure will be assigned. Total scores that are missing for any other reason will be treated as missing in calculating the composite neuropsychological test battery score.

For partially missing (item-level) missing data, if fewer than 25% of items within a NACC subtest measure are missing, scores for the missing items will be prorated as the average of the completed items on that subtest. This procedure will be employed for a maximum of two NACC subtests. If more than 25% of the items within any NACC subtest are missing, the entire subtest is missing.

The total composite neuropsychological test battery score will be calculated as the overall average Z-score from each of the completed subtests. If more than 2 NACC subtests are missing, the total composite neuropsychological test battery score will be missing.

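### As written, the exploratory neuropsychological composite averages two Trail Making times (longer is worse) with nine higher-is-better scores and never reverses them

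*SAP*

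**What the plan says.** SAP 4.8.5.2 and Appendix 3 give the same construction. There are 11 measures, each is turned into a Z-score, and "The composite outcome will comprise the overall average of the Z-scores from each of the following NACC subtest measures". Two of the 11 are "Trail Making Test A time to completion; Trail Making Test B time to completion". On standardisation the SAP says "Z-scores for each participant on each measure will be calculated using the overall average of all participants at baseline as reference". The average runs over the subtests completed, and the composite is set to missing "If more than 2 NACC Neuropsychological Test Battery subtest measures are missing".

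Appendix 3 adds a rule for inability. When a participant is "unable to complete the task for cognitive reasons, the worst possible score for the measure will be assigned".

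Protocol 9.1.4.4 fixes the direction of Trails: "Performance is judged in terms of time to complete each trial". Participants work against the clock, with maxima of 150 seconds for A and 300 seconds for B.

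On status, SAP 4.8.5.2 says "This analysis is exploratory for potential publication purposes only". SAP 4.3.4 tests exploratory endpoints without multiplicity adjustment and treats the results as descriptive.

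**The concern.** A Z-score puts measures on a common scale but keeps their direction. A long Trails time gives a high Z, and so does a good recall score. Averaging the two without a sign change makes poor Trails performance count as good performance.

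Neither document contains a reversal. The SAP does state direction for ADAS-Cog (4.8.1), CDR-SOB (4.8.2), ADCS-ADL (4.8.4.2) and MMSE (4.8.4.4), but not for this composite.

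The inability rule adds to the problem. A participant who has declined too far to do Trails receives the longest time, and an unreversed average credits that as a gain.

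What is at stake is the size and meaning of one exploratory treatment difference that may be published. The Trails part of the week 48 change would offset part of the change on the other nine measures.

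**Working it through.** Neither document gives a sample size, power or expected effect for this composite, so there is no stated figure to reproduce. The check counts directions and follows the averaging rule through.

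**Inputs**

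| Measures in SAP 4.8.5.2 | Number | Scoring (Protocol section) | Better direction |
|---|---|---|---|
| Craft Story, immediate and delayed | 2 | story units recalled (9.1.4.1) | higher |
| Benson Figure, copy and delayed | 2 | accuracy points, 0 to 17 (9.1.4.2) | higher |
| Multilingual Naming Test | 1 | items named correctly, 0 to 32 (9.1.4.3) | higher |
| Letter and category fluency | 2 | words produced in 60 seconds (9.1.4.5, 9.1.4.6) | higher |
| Number Span, forward and backward | 2 | correct trials (9.1.4.7) | higher |
| Trail Making A and B | 2 | seconds (9.1.4.4) | lower |

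That makes 9 higher-is-better and 2 lower-is-better measures.

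**Step 1: the rule in symbols.** Let x be the change on a measure in baseline SD units, with positive meaning better. For Trails, the change in the Z-score of time is -x. With all 11 measures present at both visits:

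- As written: (sum of the nine x - x_A - x_B)/11
- With Trails reversed: (sum of the nine x + x_A + x_B)/11
- Error: -2(x_A + x_B)/11

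**Step 2: equal change d on every measure.**

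- As written: (9 - 2)d/11 = 7d/11 = 0.64d
- Reversed: 11d/11 = 1.00d
- Example, a decline of 0.5 SD on all 11: (-9 x 0.5 + 2 x 0.5)/11 = -0.32 as written, against -0.50 reversed

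**Step 3: only Trails changes, both tests 1 SD slower.**

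- As written: +2/11 = +0.18, an apparent improvement
- Reversed: -2/11 = -0.18
- Gap: 4/11 = 0.36 averaged-Z units

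**Step 4: worst-score assignment.** Suppose a participant completes Trails at baseline in less than the worst time (Z = z0) and is assigned the worst time at week 48 (Z = z1). Then z1 > z0, and the component adds (z1 - z0)/11, which is positive. The participant counts as improved on that component.

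**Step 5: standardised effect (illustrative).** The documents give no correlations. Assume equal effects, equal variances and a common correlation r between the 11 changes when all are oriented so that higher is better. The variance of the sum is 11 + r((sum of signs)^2 - 11):

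- Reversed: 11 + r(121 - 11) = 11 + 110r
- As written: 11 + r(49 - 11) = 11 + 38r
- Ratio of standardised effects: (7/11) x sqrt((11 + 110r)/(11 + 38r))

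| r (assumed) | Ratio | Loss |
|---|---|---|
| 0.2 | 0.636 x sqrt(33/18.6) = 0.848 | 15.2% |
| 0.35 | 0.636 x sqrt(49.5/24.3) = 0.908 | 9.2% |
| 0.5 | 0.636 x sqrt(66/30) = 0.944 | 5.6% |

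The standardised loss is smaller than the 36% loss in Z units because the wrong sign also shrinks the composite's SD.

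**The case against.** The strongest reply is that the SAP is silent, not wrong. It never says to leave Trails unreversed, and its authors plainly know the direction: the Protocol describes a timed test, and assigning a worst score requires knowing which end is worst. A competent programmer would probably reverse the two scores without being told. The analysis is also exploratory.

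Part of this stands. The documents do not show that the composite will be computed wrongly, and a reader should not infer that it will be. The finding concerns the text. But the text is a complete recipe (list the measures, standardise, average), and followed exactly it gives two components the wrong sign. Leaving the sign to the programmer means that it could be settled after unblinding.

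Two neighbouring criticisms are tempting and should not be made:

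- **No SD is named.** A Z-score ordinarily implies division by an SD, and the SD of all participants at baseline is the natural reading.
- **Appendix 3 gives no worst value for Trails.** The Protocol maxima of 150 and 300 seconds are the obvious candidates.

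Both can be made explicit in the same edit, but neither is a defect in itself.

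**Conclusion.** The point holds as an error in the written rule for one exploratory endpoint. With complete data at both visits and equal change, the composite shows 0.64 of the true change. Slowing on Trails moves it the wrong way, by +0.18 instead of -0.18 for 1 SD on both tests. The 6% to 15% loss in standardised effect rests on assumed equal effects, equal variances and a correlation between 0.5 and 0.2.

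Four stronger readings are not supported:

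- **That trial conclusions are affected.** The composite is outside the gatekept family, so the co-primary and secondary results and the type I error control are untouched.
- **That the whole composite points the wrong way.** If the nine other measures improve by a on average and Trails by b, the result as written is (9a - 2b)/11. For positive a, this turns negative only when b exceeds 4.5a, and nothing in the documents suggests such a gap.
- **That missing subtests change the 0.64 in a fixed way** (for example 5/9 = 0.56 with two non-Trails tests missing, or 8/10 = 0.80 with one Trails test missing). Those ratios require the same tests to be missing at baseline and week 48. Otherwise the change depends on baseline levels. With nine measures at Z = -1, both Trails at +1, no true change and Trails missing only at week 48, the score goes from -7/11 = -0.64 to -1.00.
- **That the extension phase is a second consequence.** Its schedule omits 5 of the 11 measures at weeks 24 and 48 (both Benson scores, naming, Trails A and B). The composite would be missing there and no extension change score can be formed.

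**What to change.** Add to SAP 4.8.5.2 and Appendix 3, in this order:

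1. Any worst-score assignment is made on the raw score. State the values used for Trails A and B, for instance by reference to the maxima in Protocol 9.1.4.4 if those are meant.
2. Each measure is standardised to the baseline mean and SD of all participants.
3. The Trail Making A and B Z-scores are multiplied by -1 before averaging, so that a higher composite means better performance.

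This costs two or three sentences. It needs no new data and changes nothing in the conduct of the trial. It is best settled before the treatment codes are released.
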